Study staff will send an unencrypted email with instructions from the User Guide for External Azure RMS Recipients first to confirm the Veteran’s email address and help recipient to open the email message. Study team will then send a second email with the informed consent and HIPAA authorization documents attached, which will include instructions on how to securely transmit pictures or scanned images using RMS.

Once the potential participant has available hard copy or DocuSign informed consent and HIPAA authorization documents, the study staff will review the study purposes, procedures, risk, and benefits and allow time for questions. Study staff will inform Veterans that if they are assigned to the EMPOWER condition, they may voluntarily choose to taper their benzodiazepines; however, this is not required to participate in the study. This is also stated on the EMPOWER website.

Participate Compensation:

Veterans will be compensated for their time, checks for \$30 will be mailed to them 4-6 weeks after completing the baseline and 6-month assessments. Participants who complete both the baseline and 6-month assessments will receive a total of \$60.

Sample Size

The original EMPOWER study reported a more than five-fold difference in benzodiazepine cessation and reduction rates with an OR greater than 8, which converts to a Cohen’s d greater than 0.8 Tannenbaum et al., 2014) [15]. However, we powered the present study using a more conservative estimate of the intervention effect based on a recent meta-analysis of 17 clinical trials (Boumparis et al., 2017) [17] showing that computer-delivered interventions demonstrate an effect size on drug use only somewhat lower than medium (0.36).

To attain 80% power with .05 type I error rate to detect a medium effect size of 0.35 with intra-class coefficient of .008 (based on the original EMPOWER study; Tannenbaum et al., 2014) [15] for the primary outcomes of benzodiazepine cessation/reduction, 66 patients per group will be needed. Assuming an 80% six-month follow-up rate, this will require enrollment at baseline of

170 participants (i.e., 85 per group). All data will be analyzed by the study biostatistician ([name]).

Randomization

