5.5 Study Evaluations

We preregistered two primary outcomes: **cessation of benzodiazepines and dose reduction of benzodiazepines at six-month follow-up**. Cessation will be defined as the absence of a benzodiazepine prescription renewal in the six months prior to follow-up, and dose reduction will be defined as a 25% or greater decrease in benzodiazepine use that has been sustained for three months or more at follow-up. Cessation will be defined as an absence of a benzodiazepine prescription at the time of the 6-month follow-up that was sustained for three consecutive months or more. Dose reduction will be defined as a 25% or greater reduction compared with baseline sustained for three consecutive months or more. All participants who cease benzodiazepines entirely will be included in those who achieve 25% or more reduction.

Assessment of reduction in benzodiazepine use to include differing doses will be converted to lorazepam equivalents and the baseline dose will be defined as the average daily dose in the six-months prior to randomization. These data will be obtained from the CDW. We will also collect participants' self-report data on benzodiazepine use, using a six-month Timeline Followback (TLFB) method (National Institute on Drug Abuse, 2021 [18], to determine the existence of any additional benzodiazepine prescriptions (e.g., from a non-VHA provider) and/or whether any additional benzodiazepine use occurred between baseline and six-month follow-up that was not captured in the administrative data at baseline and six-month follow-up. TLFB is a valid calendar-based method that asks participants to retrospectively recall their drug use (e.g., yes, or no, daily dose) up to two years prior to the interview date (see Appendix B for copy of TLFB).

It is true that CDW prescription medication fill records may not always accurately reflect changes in Veterans' consumption of their medication. Also true is that self-report of medication use is not always accurate. Because all methods for assessing medication use have advantages and disadvantages, we will collect data both from the CDW and the TLFB and we will look at both to determine the outcome.

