Pre-registered secondary outcomes are **anxiety symptoms, sleep quality, and overall health and quality of life**. Anxiety symptoms will be measured by the Generalized Anxiety Disorder Scale (Spitzer et al., 2006) [19] (see Appendix C for copy of GAD-7). This seven-item scale asks about the presence and severity of seven symptoms of anxiety (e.g., feeling on edge, having trouble relaxing) and includes an omnibus item rating that is the extent to which any of the seven symptoms has made it difficult "to do your work, take care of things at home, or get along with other people". Items can be summed for an overall rating of anxiety symptoms. Sleep quality will be measured by the Patient-Reported Outcomes Measurement System brief sleep disturbance scale (Yu et al., 2012) [20]. This eight-item scale assesses degree of difficulty falling asleep, degree to which sleep is refreshing, and ability to stay asleep through the night. Items are summed to indicate symptom severity (see Appendix D for copy of sleep assessment).

Overall health and quality of life will be measured by the RAND Veterans Short Form-12 measure (Schalet, 2015) [21], which comprises items assessing global emotional and physical well-being and function (e.g., "How much time in the past four weeks did you have a lot of

energy?", "Compared to one year ago, how would you rate your physical health today?") (see Appendix E for copy of VR-12 form). The final secondary outcome is cessation, or 25% decrease of benzodiazepine use at 12 months; unlike the prior measurements, this will be conducted using databases only.

We will also be assessing participants alcohol use using the three-item Alcohol Use Disorders Identification Test-consumption items, readiness to change medication use using the Readiness Rule, and symptoms of benzodiazepine dependence using the Severity of Dependence Scale. These tools/scales are included in the baseline and 6-month follow-up assessments. Veteran participants will provide self-report of this information for these measures, during their baseline and 6-month interviews.

To determine whether any intervention effects on benzodiazepine use evident at six-months follow-up are maintained, data on benzodiazepine use will again be gathered at 12-month follow-up using VHA centralized databases only (resource constraints prevent assessing this by interview). No other 12-month outcome data will be gathered.

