5.6 Data Analysis

The randomization scheme will be checked by comparing key baseline measures between the experimental and the control group. If significant differences between groups are identified, we will adjust for these variables in all the models. Baseline variables that are strongly associated with the outcomes will also be included in the corresponding outcome models. Linearity between continuous variables and outcomes will be checked. If the relationship is not linear, other appropriate functional forms (e.g., quadratic) will be used or the variable will be changed to categorical. Proportions of missing values will be assessed, and a multiple imputation method will be used to impute the missing values if necessary and if the missing at random assumption is deemed reasonable.

Descriptive statistics will be calculated to examine data distributions. Tests for distributional assumptions (e.g., normality) for continuous variables will also be performed. Bivariate analyses will be performed for categorical variables using a Chi-square test, for continuous normally

distributed variables using independent t-test and for non-normally distributed continuous variables using nonparametric Wilcoxon rank-sum test.

For multivariate analysis for the main outcomes of benzodiazepine discontinuation and 25% dose reduction at follow-ups, we will use generalized estimating equations (GEE) models or generalized linear mixed models to examine the effect of EMPOWER for Veterans on the proportions of participants with discontinuation and dose reduction with logit link and compound symmetry correlation structure (in GEE) due to repeated measures within each participant. All the models will include the indicator variable for the EMPOWER for Veterans versus control conditions, time representing six- and 12- month follow-ups and covariates identified in bivariate analysis. The baseline benzodiazepine use (i.e., average daily dose) variable will also be included. The interaction between the indicator variable and time will be checked and dropped if non-significant at the significance level of 0.05.

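### The six-month primary outcomes are settled from two sources with no written rule, then modelled together with a database-only 12-month outcome

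*Combined protocol and SAP*

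**What the plan says.** The primary outcomes in section 5.5 are "cessation of benzodiazepines and dose reduction of benzodiazepines at six-month follow-up". For dose and baseline dose the section states: "These data will be obtained from the CDW". A six-month TLFB is added "to determine the existence of any additional benzodiazepine prescriptions (e.g., from a non-VHA provider) and/or whether any additional benzodiazepine use occurred" that the administrative data missed. The section then concedes that fill records and self-report can each be wrong, and closes: "we will collect data both from the CDW and the TLFB and we will look at both to determine the outcome". It gives no order of precedence, no rule for conflict and no rule for a participant without a TLFB.

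The sample size in section 5.1 is set "Assuming an 80% six-month follow-up rate". Under Participant outreach (section 5.5), people who cannot be reached by phone are mailed the assessment, and those who still do not respond count as lost to follow-up.

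Of the 12-month benzodiazepine outcome, section 5.5 says: "unlike the prior measurements, this will be conducted using databases only". Section 5.6 fits one GEE or mixed model per outcome, with "time representing six- and 12- month follow-ups", and removes the arm-by-time interaction if it is not significant at 0.05. No sensitivity analysis by source is described.

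On blinding, section 5.1 (Randomization) covers only the principal investigators. Participants are told their arm, and approved study staff can reach the allocation sequence.

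**The concern.** Three things are left open or mixed.

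- **Classification.** With two fallible sources and no rule, each discordant case needs a judgement. The plan does not say who makes it or whether that person knows the arm.
- **Time.** The six-month outcome can use two sources and the 12-month outcome only one. A model that treats them as repeated measures of one variable attributes the difference in source to time. This bears directly on whether effects are maintained at 12 months.
- **Arm.** Once the interaction is dropped, a single arm effect is reported across two differently measured outcomes. It is biased if the sources disagree more often in one arm, or if one arm is interviewed more often. Both are plausible: participants know their arm, and the website offers a tablet-by-tablet self-taper calendar, so consumption and fills may part company mainly in the intervention arm.

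**Working it through.** **The plan's own figures.** 85 per group × 0.80 = 68, which covers the stated need of 66. Over both arms, 170 × 0.80 = 136 would have a TLFB at six months and 34 would not. At 12 months nobody has one. Of 2 × 170 = 340 planned records in the joint model, 136 (40%) can draw on both sources.

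**Assumptions (not in the documents).** c is the CDW cessation rate. q is the share of CDW cessations that the TLFB overturns among those interviewed. f = 0.80 is the share interviewed. True status does not change between 6 and 12 months. The plan does not say how people without a TLFB are classified, so two readings are shown:

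- A: classified from CDW; observed six-month rate = c(1 − fq)
- B: left out, or imputed to resemble those interviewed; observed rate = c(1 − q)

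The 12-month rate is c under either reading.

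**Change of source read as change over time.** OR (12 v 6) = [c/(1 − c)] ÷ [p6/(1 − p6)], where p6 is the observed six-month rate.

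| c, q | p6 (A) | OR (A) | p6 (B) | OR (B) |
|---|---|---|---|---|
| 0.10, 0.10 | 0.092 | 1.10 | 0.090 | 1.12 |
| 0.30, 0.30 | 0.228 | 1.45 | 0.210 | 1.61 |

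For the second row under A: (0.30/0.70) ÷ (0.228/0.772) = 0.4286 ÷ 0.2953 = 1.45. The OR rises with both c and q, so these rows bound the range.

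**Arm effect at six months.** Take CDW cessation of 20% (intervention) v 10% (control): OR = (0.20/0.80) ÷ (0.10/0.90) = 2.25, which is also the 12-month OR.

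| q, intervention v control | Rates (A) | OR (A) | Rates (B) | OR (B) |
|---|---|---|---|---|
| 30% v 10% | 0.152 v 0.092 | 1.77 | 0.140 v 0.090 | 1.65 |
| 10% v 30% | 0.184 v 0.076 | 2.74 | 0.180 v 0.070 | 2.92 |
| 20% v 20% | 0.168 v 0.084 | 2.20 | 0.160 v 0.080 | 2.19 |

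**Unequal interview rates with no arm effect (reading A).** With 70% v 90% interviewed, the rates are c(1 − 0.7q) v c(1 − 0.9q). At c = q = 0.10 this is 0.093 v 0.091, OR 1.02. At c = q = 0.30 it is 0.237 v 0.219, OR 1.11.

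**Would the interaction test catch it?** The shift from 2.25 to 1.77 is ln 2.25 − ln 1.77 = 0.811 − 0.571 = 0.240. With 85 per arm at 20% v 10%, the variance of one log OR is 1/17 + 1/68 + 1/8.5 + 1/76.5 = 0.204. Using that variance at both times and an assumed correlation ρ between the two log ORs, the SE of the difference is √[2 × 0.204 × (1 − ρ)]. At ρ = 0.5 this is 0.45, so z = 0.53; at ρ = 0.9 it is 0.20, so z = 1.2. A shift of that expected size sits well short of 1.96, and the term would usually be dropped.

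Only overturned successes are modelled here. The closing sentence of section 5.5 would also let self-report turn a filled prescription into a reduction, which pushes in the other direction.

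**The case against.** The strongest reply is that section 5.5 is less open than its closing sentence suggests. It defines cessation by prescription, takes dose data from the CDW and gives the TLFB a directional job, finding extra use. It also labels the 12-month outcome openly as secondary and database-only, and section 5.6 includes a time term. A source shift common to both arms goes largely into that term: in the equal-overturn row above, the arm OR moves only from 2.25 to 2.20. This all stands. It limits the arm-effect concern to differential disagreement or interview rates, but supplies neither the missing rule nor a clean 6-versus-12-month comparison.

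Three stronger readings are tempting, and the documents do not support them.

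- A reader might infer that staff who know the allocation classify the outcome. The plan does not name the classifier. Blinding of that step is unspecified, not stated to be absent.
- A reader might infer that the roughly 20% not reached are classified from the CDW alone. The plan calls non-responders lost to follow-up, and section 5.6 allows multiple imputation. The 80% is itself a planning assumption that the mailed form may raise, and the text does not say whether that form includes the TLFB.
- A reader might size the problem by resolving every discordant case one way in one arm and the opposite way in the other. That gives a ceiling, not an estimate, and is not used here.

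It is also fair to say that a CDW-only outcome is a trade-off. Section 5.5 itself warns that fills may not track consumption, and someone splitting tablets may cut consumption while fills continue.

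**Conclusion.** The concern holds in this form: the plan gives no precedence, conflict or missing-TLFB rule for its primary outcomes and no statement that classification is blind to arm. It then pools a mixed-source six-month outcome with a database-only 12-month one.

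The 6-versus-12-month comparison is confounded with source whenever the TLFB changes any classification. Under the assumed ranges, and with non-interviewed participants classified from the CDW, the spurious odds ratio is 1.10 to 1.45; it is larger if they are left out. Bias in the arm effect is conditional: material if disagreement differs by arm (2.25 becoming 1.77 or 2.74), small if it does not (2.20). The cessation, overturn and unequal interview rates are illustrative, since the documents give none of them. This should be settled in the plan, but it does not show that the trial's result will be wrong.

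**What to change.** 1. Derive a CDW-only outcome with one algorithm at 6 and 12 months, for all randomized participants whose data may be used (section 5.7 removes those who withdraw and decline). Use it for the joint 6/12-month model and the maintenance comparison. Section 5.5 words cessation in two ways, so the algorithm must state which applies.
2. If a combined CDW and TLFB outcome is kept, analyse it at six months only. Write the rule down, keep it consistent with the TLFB purpose stated in section 5.5 (finding additional prescriptions or use), cover participants without a TLFB, and have it applied by someone without the arm code.
3. Report CDW-only, combined and TLFB-only results at six months, and state which is primary before outcomes are examined by arm.

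The cost is some plan wording and a few extra analyses of data already being collected. As the outcomes are preregistered and the trial is under way, the clarification should be dated and documented. CDW-only results miss non-VA use and reduced consumption while fills continue; the combined and TLFB-only analyses are there to address those gaps.

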5.6 Data Analysis

The randomization scheme will be checked by comparing key baseline measures between the experimental and the control group. If significant differences between groups are identified, we will adjust for these variables in all the models. Baseline variables that are strongly associated with the outcomes will also be included in the corresponding outcome models. Linearity between continuous variables and outcomes will be checked. If the relationship is not linear, other appropriate functional forms (e.g., quadratic) will be used or the variable will be changed to categorical. Proportions of missing values will be assessed, and a multiple imputation method will be used to impute the missing values if necessary and if the missing at random assumption is deemed reasonable.

Descriptive statistics will be calculated to examine data distributions. Tests for distributional assumptions (e.g., normality) for continuous variables will also be performed. Bivariate analyses will be performed for categorical variables using a Chi-square test, for continuous normally

distributed variables using independent t-test and for non-normally distributed continuous variables using nonparametric Wilcoxon rank-sum test.

For multivariate analysis for the main outcomes of benzodiazepine discontinuation and 25% dose reduction at follow-ups, we will use generalized estimating equations (GEE) models or generalized linear mixed models to examine the effect of EMPOWER for Veterans on the proportions of participants with discontinuation and dose reduction with logit link and compound symmetry correlation structure (in GEE) due to repeated measures within each participant. All the models will include the indicator variable for the EMPOWER for Veterans versus control conditions, time representing six- and 12- month follow-ups and covariates identified in bivariate analysis. The baseline benzodiazepine use (i.e., average daily dose) variable will also be included. The interaction between the indicator variable and time will be checked and dropped if non-significant at the significance level of 0.05.

The same method will be used to examine any impact of the intervention on the three secondary outcomes at baseline and six-month follow-up (anxiety, sleep quality, and quality of life) with identity link and the same correlation structure if the normality assumption is met. Should the normality assumption be violated, other distributions and link functions will be specified. The models will include the same indicator variable for EMPOWER for Veterans versus the control condition, time for baseline and 6-month follow-up and covariates identified in bivariate analysis. Same interaction term will be checked and dropped if non-significant. SAS 9.4 will be used in all the analyses.

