Aim 1 has been completed. A promising non-VA benzodiazepine cessation intervention (EMPOWER) has been converted from paper & pencil to an electronic format tailored to Veterans. Aim 2, conduct a **randomized clinical trial of the effectiveness of the tailored, electronic intervention (EMPOWER for Veterans) on VA primary care patients' benzodiazepine cessation/reduction and functional outcomes is being implemented**. A third aim will seek to conduct a budget impact analysis to estimate the costs of implementing EMPOWER for Veterans throughout VA. The Palo Alto, CA site will conduct Aim 3 and thus seek approval for related study activities at their site. **This protocol seeks approval for Aim 2 of this research study.**

Innovation

Converting the effective use of the paper-and-pencil version of EMPOWER to an electronic version that works on smart phones, tablets, and/or desktop computers, the proposed project intends to tailor the electronic version (EMPOWER for Veterans) to the needs and preferences of the Veteran population; in effect reducing risks among this population of benzodiazepine users.

Methodology

When EMPOWER for Veterans is fully designed, its effectiveness will be evaluated in a two-arm individually randomized controlled trial with 170 Veterans at the Central Arkansas Veterans Healthcare system and the Minneapolis VA Health Care System, and affiliated sites. Veterans who have been taking benzodiazepines for at least 3 months and have access to a smartphone or desktop/laptop computer will be invited to participate. The primary hypothesis of the study is that Veterans receiving EMPOWER for Veterans will be significantly more likely to cease benzodiazepine use entirely and reduce their dose by at least 25% at 6-month follow-up than the control group. The secondary hypothesis is that Veterans receiving EMPOWER for Veterans will also experience fewer anxiety symptoms, better sleep quality, and overall health/quality of

life at 6-month follow-up. A supplemental analysis of benzodiazepine use only will be conducted at 12 months, using VA databases to evaluate whether changes identified persist over time.

Impact

Considering that electronically delivered interventions are inexpensive to disseminate once they have been developed, this project has an excellent chance to promote health care value by creating an easily scaled-up, method of reducing the prevalence of the widespread risk of long-term benzodiazepine use to improve Veterans' health.

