To tailor EMPOWER to the veteran population, our research team worked with VHA patients, physicians, and administrators; we then worked with software developers to convert the intervention to a computer-delivered format we call EMPOWER for Veterans (Electronic Version). This protocol describes how EMPOWER for Veterans will be tested in a randomized clinical trial evaluating whether it is effective with a markedly different population and format than in the initial Canadian study. The primary hypotheses of the RCT are that long-term users of benzodiazepines who are assigned to receive EMPOWER for Veterans will be significantly more likely than controls to cease taking benzodiazepines or reduce their benzodiazepine dose by at least 25% at six-month follow-up. The secondary hypotheses are that relative to controls, participants receiving EMPOWER for Veterans will improve more on anxiety symptoms, sleep quality, and overall health/quality of life at six-month follow-up. As functional outcomes were not measured in the original EMPOWER study, this is a unique contribution of the present trial. In addition to being important in themselves, these three secondary outcomes may moderate or mediate participants' response to EMPOWER for Veterans. For example, if secondary outcomes improve upon benzodiazepine tapering, participants may be more likely to continue to full cessation. In contrast, if functional outcomes deteriorate, patients and their physicians may be inclined to abandon EMPOWER for Veterans; if this were a common result it would likely reduce the adoption of EMPOWER for Veterans within VHA. Also, part of our secondary analysis will be to explore whether any effects of EMPOWER for Veterans observed on our primary outcomes at six-month follow-up are maintained at 12-month follow-up.

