3.0 Objectives

The overall goal of this project is to create an electronic version of EMPOWER tailored to Veterans receiving VHA primary care. Specifically, this study maintains three aims. This protocol is specific to Aim 2, which is described in detail as the following:

Aim 2: Conduct a randomized clinical trial to test the effectiveness of the tailored, electronic intervention (EMPOWER for Veterans) on VA primary care patients' benzodiazepine cessation/reduction and functional outcomes at follow-up.

The primary hypotheses of Aim 2 are that in a clinical trial of 170 Veterans who are long-term users of benzodiazepines, those receiving the EMPOWER for Veterans intervention will be significantly more likely at 6-month follow-up to (a) cease taking benzodiazepines entirely, and (b) reduce their benzodiazepine dose by 25% or more. A secondary hypothesis of Aim 2 is that, relative to controls, Veterans receiving EMPOWER for Veterans will improve more on three functional outcomes: anxiety, sleep quality, and overall health/quality of life.

This protocol only describes Aim 2 research activities, which will occur at the Central Arkansas Veterans Health Care System; and as a result, IRB approval is being requested to conduct Aim 2 only.

We plan to request approval for Aim 3 at the Palo Alto Veterans Healthcare System, since the work for that aim will be conducted at that site.

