Participants randomized to the EMPOWER condition will be provided information about how to dispose of any unwanted benzodiazepines should they choose to reduce or discontinue their medication. Specifically, we will share with the participant that they may contact their primary care doctor to obtain a Medication Disposal Patient Kit and/or identify nearby locations (via the website artakeback.org) for the Arkansas medication takeback program.

To produce the taper schedule, participants will enter their current benzodiazepine dosage into the EMPOWER website. A tapering schedule will then be generated based on the self-reported number of tablets that the patient is taking each time they take their medication. The tapering schedule will last up to 21 weeks with each day's target pill consumption graphically displayed on a calendar (e.g., full-pill, half-pill, quarter pill, or no pill).

The EMPOWER for Veterans website will also include practical tips for managing the taper process including when to contact one's primary care physician, along with CAVHS and Minneapolis VA pharmacy contact information. Study Participants will be notified of need to obtain a pill cutter along with instructions to contact pharmacy to obtain pill cutter if they do not already have one. The study team will not be providing pill cutters to study participants. We learned from the previous Aim 1 focus groups with Veterans, that most Veterans know how to

obtain a pill cutter on their own since they are easily and cheaply obtainable online or through pharmacies.

Control condition

Participants assigned to the control condition will be asked to continue to follow any provider recommendations regarding benzodiazepine use (i.e., treatment-as-usual). Control participants will also be informed that access to the EMPOWER for Veterans materials will be made available to them at the end of the study (i.e., at 12-months post randomization).

Data Collection

Participants in both conditions will be asked to complete a baseline and 6-month assessment. We also plan to collect data from the CDW on participants' benzodiazepine use at baseline, six-month and 12-month follow-up.

Risks:

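### The primary hypotheses are at 6 months, but the model for the main outcomes pools 6 and 12 months, may drop arm-by-time, and names no 6-month contrast as primary

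*Combined protocol and SAP*

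**What the plan says.** Section 3.0 states the primary hypotheses as EMPOWER recipients being "significantly more likely at 6-month follow-up to (a) cease taking benzodiazepines entirely, and (b) reduce their benzodiazepine dose by 25% or more". Section 2.0 also sets them at six months, and section 5.5 lists the primary outcomes as "cessation of benzodiazepines and dose reduction of benzodiazepines at six-month follow-up".

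The 12-month result has lower status throughout. The abstract (Methodology) says "A supplemental analysis of benzodiazepine use only will be conducted at 12 months". Section 2.0 makes it part of the secondary analysis, to "explore whether any effects of EMPOWER for Veterans observed on our primary outcomes at six-month follow-up are maintained at 12-month follow-up". Section 5.5 says "The final secondary outcome is cessation, or 25% decrease of benzodiazepine use at 12 months".

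Section 5.6 gives one specification for the two main outcomes, a GEE or generalized linear mixed model with logit link: "All the models will include the indicator variable for the EMPOWER for Veterans versus control conditions, time representing six- and 12- month follow-ups", plus covariates and baseline average daily dose. It then says: "The interaction between the indicator variable and time will be checked and dropped if non-significant at the significance level of 0.05". The last paragraph of section 5.6 applies the same check-and-drop rule to anxiety, sleep and quality of life, modelled at baseline and 6 months.

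**The concern.** Once arm-by-time is removed, the model has a single arm coefficient, so a secondary time point enters the primary test. Which quantity is tested depends on an interaction p-value seen in the trial's own data. If the term is kept, a 6-month contrast can be estimated, but the plan does not call it primary. The chi-square test in the same section is bivariate, is tied to no outcome or time, and is not called primary either.

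At stake is what a positive primary result means. A significant shared coefficient could be read as success on a 6-month hypothesis when the effect arose later, and a 6-month effect that fades would be understated.

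**Working it through.** **The plan's own figure.** Section 5.1 (Sample Size) gives 66 per group for effect size 0.35, 80% power, alpha .05 and intra-class coefficient .008, and enrols 85 per group for 80% follow-up (66/0.8 = 82.5). The usual two-group formula does not return 66: 2 × (1.96 + 0.8416)² / 0.35² = 128.1 per group. The derivation of 66 is not stated. I use 66 below only as the analysed number per arm.

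**Inputs.** From the documents: 66 per arm, effect size 0.35, alpha .05 (taken as two-sided), logit link, compound symmetry, and the 0.05 drop rule. Assumed, because the documents give no rates or correlations: control rates of 10, 15 and 20% at both times, and latent within-person correlation of 0.5 to 0.9 (about 0.20 to 0.68 on the GEE scale).

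**Effect on the odds scale.** OR = exp(0.35 × π/√3) = 1.887, so log OR = 0.635. Treated rates are then 17.3, 25.0 and 32.0%.

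**How often the term is dropped when the effect vanishes by 12 months.** The variance of the interaction is the sum over arms of v6 + v12 − 2ρ√(v6·v12), where v = 1/[n p(1−p)].
- Control 10%, ρ = 0.20: SE = 0.700; 0.635/0.700 = 0.91; non-significant in 85% of trials.
- Control 20%, ρ = 0.68: SE = 0.338; 0.635/0.338 = 1.88; non-significant in 53%.

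**The whole procedure, simulated.** Exchangeable logit GEE with robust Wald tests and a standardised baseline dose (assumed latent loading 0.3), 4,000 trials per cell, Monte Carlo SE at most 0.8 points. The planned rule takes the shared coefficient if the interaction has p ≥ 0.05, and otherwise the 6-month coefficient. Ranges run over the assumed rates and correlations.

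| True OR at 6 / 12 months | Planned rule rejects | 6-month contrast rejects | Shared OR | 6-month OR estimate |
|---|---|---|---|---|
| 1 / 1.89 (extreme) | 11.4-16.3% | 2.9-4.9% | 1.45-1.56 | true value 1.0 |
| 1.37 / 1.89 | 15.7-31.7% | 7.0-12.5% | 1.67-1.72 | 1.39-1.44 |
| 1.89 / 1 (extreme) | 18.5-31.3% | 20.9-36.9% | 1.45-1.57 | 1.95-2.00 |
| 1.89 / 1.89 | 27.2-53.5% | 21.5-37.0% | no bias | no bias |
| 1 / 1 | 4.9-6.3% | 3.6-5.1% | no bias | no bias |

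In simulation the term is dropped in 54-85% of trials in the first row and 53-85% in the third, which agrees with the closed form. In the first row, rejections favouring EMPOWER are 9.9-14.0% against 1.7-2.6% (model without baseline dose). The mixed-model option, with correlation 0.5-0.7 and no covariates, shows the same pattern: 9-14% against 3-5% in the first row and 12-28% against 14-34% in the third.

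**Are unequal effects plausible?** The plan leaves maintenance open. For cessation, section 5.1 says "The tapering schedule will last up to 21 weeks", and section 5.5 gives two definitions. If three sustained months are counted from the end of a full-length taper, 21 + 13 = 34 weeks, which is past week 26. If any renewal in the preceding six months disqualifies, one renewal during the taper rules out 6-month cessation. On those readings a long taper may count at 12 months but not at 6. A 25% reduction can be reached during the taper, so for that outcome fading is the more relevant case.

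**Functional outcomes.** In a baseline and 6-month linear model with balanced data and no interaction, the arm coefficient is the average of the two between-arm differences. With equal arms at baseline and a difference δ at 6 months, it is (0 + δ)/2 = δ/2. The between-arm difference in change, which is what the secondary hypothesis concerns, is no longer in the model.

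**The case against.** Dropping a non-significant interaction is conventional. If the effect is constant, the planned rule is unbiased and has about 5 to 17 points more power than a 6-month contrast. With no effect at either time, rejection stays near 5-6%. Even under complete fading, power falls by only about 2 to 6 points. All of this stands, but it does not tell the reader which quantity is primary, and it does not remove the distortion of the odds ratio when effects differ.

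Some stronger readings go further than the documents allow:
- A reader might infer that the plan has no means of addressing maintenance. The interaction is to be checked, and that is a test of change between 6 and 12 months. It is weak, and a non-significant result is not evidence that effects are maintained.
- A reader might infer that a full-length taper can never count as cessation at 6 months. Twenty-one weeks is a maximum, the definitions rest on prescriptions or renewals, and someone tapering from tablets already supplied may have no prescription well before week 21. Self-report is also used, with no stated rule for combining it with the database.
- A reader might take 11-16% as the false-success rate. It counts both directions, in an extreme case.
- A reader might infer that 66 was sized for a two-time-point average, because 128.1 × 1.008 / 2 = 64.6. The documents do not say so. The coefficient is attributed to the original EMPOWER study, whose listed title calls it a cluster randomized trial, and treating about 129 as a total rather than per group gives a similar number.

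**Conclusion.** The point holds. The hypotheses and outcomes are at 6 months; the only model specified for them pools 6 and 12 months under a data-driven rule and leaves the primary contrast unnamed. That much follows from the text and needs no assumed rates. The size does depend on assumptions (control rates 10-20%, OR 1.89, latent correlation 0.5-0.9, 66 per arm at both times). In the two extreme cases, rejection of a true 6-month null rises from 3-5% to about 11-16%, or a 6-month OR near 1.9 is usually reported as about 1.5. In the intermediate case the shared OR is about 1.7 against about 1.4. Unequal effects are plausible, not established. It should be settled before analysis, because the choice cannot credibly be made after the interaction p-value is known.

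**What to change.** In section 5.6, for the main outcomes:
1. Keep arm-by-time whatever its p-value, or fit a 6-month-only model.
2. Name the 6-month arm contrast, adjusted for baseline average daily dose, as the primary test for each primary outcome.
3. Report the 12-month contrast, and the change in effect from 6 to 12 months with its confidence interval, as secondary. Do not present a non-significant interaction as maintenance.

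In the last paragraph of section 5.6, keep arm-by-time for the three functional outcomes and name the between-arm difference in change as the quantity tested.

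This is a wording change using data already planned. Its statistical cost should be disclosed: if the effect is constant, power is lower (about 21-37% against 27-53%).

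As a separate matter, section 5.1 should state power for the 6-month binary contrast with its assumed control rate, and how 66 was obtained. With p̄ the mean of the two rates, power = Φ{[(pT − pC) − 1.96√(2p̄(1−p̄)/n)] / √([pC(1−pC) + pT(1−pT)]/n)}. At OR 1.89 and n = 66 this gives 23, 30 and 35% for assumed control rates of 10, 15 and 20%. If database status is available for all 85 per arm, it gives 28, 37 and 43%.
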